Patient safety: All potential side effects of calcium will be recorded as part of this study, including flushing, arm discomfort, nausea, vomiting, bradycardia, tachycardia, arrhythmia, and hypertension. A single dose of dilute CaCl_2 , infused slowly through an intravenous (IV) line in the sensate upper extremity of an un-sedated patient, is unlikely to cause severe adverse effects. The major concern with CaCl_2 is tissue necrosis from extravasation. Any discomfort in the IV site will warrant immediate study drug infusion discontinuation with careful assessment of the extremity. The clinical anesthesiologist caring for the patient will also monitor for potential hemodynamic consequences of calcium infusion including bradycardia, hypotension, or hypertension. The anesthesiologist providing care to the patient will be instructed to assume the study drug contains 1 gram of CaCl_2 for all cases, and to immediately discontinue the infusion if they believe any the patient may be having a severe adverse effect. A data safety monitoring committee of two attending anesthesiologists with no involvement in the trial and with a track record of data safety monitoring has been created for this trial. Any potential adverse events including patient hemodynamic compromise or concern for drug extravasation will be reviewed immediately ad hoc, and they will determine whether unblinding is required and when the study may resume.

Management of hypercalcemia: Acute hypercalcemia may manifest as altered mental status, bradycardia, or hypotension. We do not anticipate clinical hypercalcemia given the patient population (young, healthy, renal dysfunction and digoxin use are contraindications), the dilute and slow infusion, the single dose of calcium, and the excellent patient tolerance and peak ionized calcium levels obtained during our pilot study. However, management of acute hypercalcemia would include immediately pausing the infusion if still running, administering a fluid bolus of 500mL to 1000mL isotonic fluid, and obtaining a serum calcium level at the discretion of the clinical anesthesia team. If necessary, the team could consider additional administration of 10-20mg intravenous furosemide to lower serum calcium further if needed.

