Feasibility: Stanford Children's Hospital performs 4600-4700 deliveries per year, of which 1600-1950 are cesarean. More than 400 cesarean deliveries per year meet study inclusion criteria. Without dedicated funding or research staff, we were easily able to enroll 40 patients in the pilot study in a 1-year time period. Plans for the study have been accepted by the group of 15 fellowship trained obstetric anesthesiologists who cover labor and delivery, all of whom participate in monthly division research meetings and are well-versed in study protocol for any actively recruiting studies. In addition, we have the support and collaboration of an excellent obstetric division. There are no concurrent competing studies in this study cohort.

Potential difficulties: Given our successful pilot, we believe this study will proceed smoothly but are ready for unanticipated problems. We have received support from obstetricians, the quantitative sciences unit (statistics), and labor and delivery nursing for the study. The greatest source of potential difficulties involves enrollment of 120 patients at a single site during a pandemic. We have infrastructure in place to allow research assistants obtain consent remotely utilizing iPads if necessary. In addition, we have obtained a letter of commitment from a second site at Brigham and Women's Hospital if needed to facilitate enrollment.

Weaknesses: The primary outcome (QBL) and secondary outcome of NRS_{UT} are surrogate outcomes for clinical endpoints of major morbidity or mortality but allow for a more reasonable study sample size for a single center.

SPECIFIC AIM 2 OVERVIEW: Serial venous blood sampling for ionized calcium level in willing study participants will allow us to also establish the PK/PD of CaCl₂ in term parturients. PK findings have applicability to a variety of clinical indications for calcium in pregnant patients, while PD will enhance mechanistic understanding of the impact of serum ionized calcium level upon uterine contractility.

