- Patient received oxytocin infusion for labor induction or augmentation.
- Patient still wants to participate and has signed consents

Please confirm this patient has NO EXCLUSIONS:

- Patient does not have renal dysfunction with serum Cr>1.0 mg/dL
- Patient does not have any known cardiac conditions
- Patient is not receiving a calcium channel blocker (none in last 24 hours)
- Patient is not receiving digoxin for a maternal or fetal indication
- This is not an emergency in which participation in the study could hinder or delay care

Study drug:

- The syringe contains **60mL saline with 1-gram Calcium Chloride OR 60mL saline placebo**
- Administer via syringe pump and microbore tubing over 10 minutes
 - Program a basic infusion on Alaris pump for basic infusion, **360mL/hr**
 - Attach microbore tubing to injection port closest to the patient
 - Start infusion **2 minutes after fetal delivery** (1 minute after cord clamp)
- Assume that every infusion contains 1 gram of calcium and **discontinue** if concerns for extravasation (arm pain and redness or signs of infiltration), hemodynamic compromise (bradycardia and hypotension most common). Contact [name] via email or cell [contact] for any concerns and document on next page.

PLEASE FILL OUT ALL INFORMATION ON THE NEXT PAGE.

STUDY ID NUMBER (on study drug syringe): _____

USE EPIC COMPUTER CLOCK FOR ALL TIMES

Fetal Delivery and oxytocin 2 unit bolus :

Time: _____

2 minutes after fetal delivery:

• Ask obstetrician to rate uterine tone 0-10: Tone: _____

• Start study drug infusion: Time Started: _____

• *If infusion was paused or stopped* Time paused: _____

Time restarted: _____

7 minutes after fetal delivery:

• Ask obstetrician to rate uterine tone 0-10: Tone: _____

12 minutes after fetal delivery:

• Ask obstetrician to rate uterine tone 0-10: Tone: _____

19 minutes after fetal delivery:

• Ask obstetrician to rate uterine tone 0-10: Tone: _____

Side effects (did the patient experience any of the following possibly related to the study drug? Circle Yes/No)

- Arm or IV site discomfort? YES / NO
- Concern for extravasation? YES / NO
- Heart rate change or arrhythmia? YES / NO Describe: _____
- Hypertension or hypotension YES / NO Describe: _____
- Flushing YES / NO
- Abnormal sensations or tastes YES / NO Describe: _____
- Nausea YES / NO
- Vomiting YES / NO
- Other YES / NO Describe: _____

Was the infusion started exactly 2 minutes after fetal delivery? YES / NO

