If not, please explain why: _____

Was the whole infusion given? If not or if paused, please explain why below

STUDY ID NUMBER (on study drug syringe): _____

If patient consents to up to 6 lab draws of 0.5mL venous blood:

- Research staff (fellow or research assistant) to analyze samples in a **different operating room**.
- **DO NOT** participate in patient care or converse with staff or the patient in the delivery room other than to obtain permission to obtain blood samples, as your knowledge of these lab values could compromise blinding of the patient, anesthesiologist, or obstetrician.

Times to target for blood samples relative to the start of study drug infusion:

• Baseline (prior to study drug start)	• 10-30 minutes
• 0-5 minutes	• 30-60 minutes
• 5-10 minutes	• 60-240 minutes

Carefully document the time that the blood was drawn using **EPIC computer clock** for each sample.

Use the **research iSTAT machine** and research EG7+ cartridges.

For patient ID on the iSTAT, please enter the study ID number and not the MRN

Time study drug started: _____

Baseline: Time: _____ pH: _____

iCa: _____

Sample 2: Time: _____ pH: _____

iCa: _____

Sample 3: Time: _____ pH: _____

iCa: _____

Sample 4: Time: _____ pH: _____

iCa: _____

Sample 5: Time: _____ pH: _____

iCa: _____

Sample 6: Time: _____ pH: _____

iCa: _____

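### The Appendix 3 bedside sheet does not carry over the protocol's rule to stop for any IV-site discomfort and assess the extremity

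*Combined protocol and SAP*

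**What the plan says.** **Patient safety (Specific Aim 1).** The section says the major concern with calcium chloride "is tissue necrosis from extravasation". Its rule for the IV site is: "Any discomfort in the IV site will warrant immediate study drug infusion discontinuation with careful assessment of the extremity". The same section gives the treating anesthesiologist a general instruction to treat every syringe as active drug and "to immediately discontinue the infusion if they believe any the patient may be having a severe adverse effect".

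**Appendix 3 Protocol Sheet, study drug block.** The sheet gives the delivery instruction, "Administer via syringe pump and microbore tubing over 10 minutes", with a pump rate of 360 mL/hr. Its stop line says to discontinue "if concerns for extravasation (arm pain and redness or signs of infiltration") or for hemodynamic compromise, and to contact the study team with any concerns.

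**Appendix 3 Protocol Sheet, side-effect list.** Arm or IV-site discomfort and concern for extravasation are two separate yes/no items. Neither carries an instruction to stop or to examine the limb.

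**The concern.** The Patient safety section relies partly on the infusion going into an arm with normal feeling in a patient who is not sedated. The patient's report of discomfort is therefore the early warning, and the rule acts on it without asking anyone to judge its cause. The sheet sets out the pump rate, the start time and the stop criteria, and it is completed for each syringe. It is likely to be the text at hand during a ten-minute infusion, and it does not state that rule.

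A clinician following the sheet as worded could record discomfort, judge that it does not suggest extravasation, and let the infusion run. The protocol requires a stop and an examination of the limb in that situation. What is at stake is participant safety, not the estimate of treatment effect.

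**Working it through.** The plan states no figure to reproduce on the stop rule itself, so the check is a comparison of texts, followed by simple dose arithmetic.

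**1. Which situations trigger a stop?** The sheet's parenthesis can be read as a joint definition (pain together with redness, or else infiltration) or as a list of examples.

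| Situation | Patient safety rule | Sheet, as definition | Sheet, as examples |
|---|---|---|---|
| Arm pain at the IV site with redness | Stop and assess | Stop | Stop |
| Arm pain at the IV site, no redness or infiltration | Stop and assess | Not triggered | Stop |
| IV-site discomfort not judged to be arm pain or a concern for extravasation | Stop and assess | Not triggered | Not triggered |
| Signs of infiltration, no complaint | Not named in the discomfort rule | Stop | Stop |

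The second row separates the two readings. The third row is a gap on both. In the fourth row the sheet goes further than the protocol's sentence, so the two triggers overlap and neither contains the other.

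**2. Is discomfort already covered by concern for extravasation?** The sheet's own side-effect list separates them. A user can answer yes to discomfort and no to extravasation concern, which is the third row.

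**3. Is assessment of the extremity anywhere on the sheet?** There is no such instruction. Looking for redness or infiltration implies some inspection before deciding to stop. It is not the careful assessment that the protocol attaches to stopping.

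**4. Does other text restore the rule?** The Feasibility paragraph says the local anesthesiologists "are well-versed in study protocol for any actively recruiting studies", but it does not mention this rule. That statement concerns the local group and would not cover staff elsewhere. Under Potential difficulties, the plan adds that "we have obtained a letter of commitment from a second site", to be used if needed. The general instruction to the anesthesiologist in Patient safety is triggered by a suspected severe adverse effect, which is also narrower than any discomfort.

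**5. How much drug does a delayed stop deliver?** Inputs are 1 g in 60 mL (Subject exposures; Appendix 3) and 360 mL/hr (Appendix 3).

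- Volume rate: 360 / 60 = 6 mL/min. This reproduces the stated duration: 60 / 6 = 10 minutes.
- Concentration in the calcium arm: 1000 / 60 = 16.7 mg/mL.
- Dose rate: 6 × (1000 / 60) = 100 mg/min, or 10% of the dose per minute.

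The documents do not say how long a stop might be delayed. Over an assumed range:

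| Assumed delay (min) | Further volume (mL) | Further CaCl2, calcium arm (mg) |
|---|---|---|
| 0.5 | 3 | 50 |
| 1 | 6 | 100 |
| 2 | 12 | 200 |
| 3 | 18 | 300 |

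These are amounts infused. They are not amounts extravasated, and they do not measure harm.

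**The case against.** The strongest reply is that the gap is narrow. If the parenthesis gives examples, arm pain is itself a named reason to stop, and what is left is discomfort too mild to be called pain or to raise concern. That stands, and it limits the size of the point. It is also true that the sheet covers infiltration without a complaint, which the protocol's discomfort rule does not name.

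Several safeguards reduce the chance that discomfort is ignored. Staff are told to assume every syringe contains calcium and to contact the study team with any concerns. The discomfort item sits directly above the extravasation item on the form. The safety committee reviews any concern for extravasation at once, although that review follows the event. The protocol body is not overridden by a form that it describes as something for research staff to complete. None of this puts the rule on the sheet, but together it makes the failure possible rather than likely.

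A reader might infer that the sheet tells staff to continue through discomfort, or that its trigger is narrower than the protocol's in every respect. The documents support neither. The sheet never says to continue, its reference to concerns for extravasation leaves room to stop, and its infiltration trigger goes beyond the discomfort rule.

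**Conclusion.** The point holds as a small patient-safety inconsistency between the protocol and a form used during the case. The sheet lacks the any-discomfort trigger and the instruction to assess the extremity. How wide the first gap is depends on how the parenthesis is read; the second is present on either reading.

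The dose figures follow from the stated concentration and pump rate, but the delays are assumed. The documents give no rate of IV-site discomfort, of extravasation given discomfort, or of clinicians continuing. A reader might infer a number of patients harmed, and none can be derived. Nor does the point reach the trial's conclusions: the primary comparison of blood loss is by intention to treat, and neither it nor the power calculation depends on this line of the sheet.

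**What to change.** Change the extravasation part of the sheet's stop line to: *Discontinue immediately for any IV-site discomfort, signs of infiltration, or any other concern for extravasation (such as arm pain or redness), and assess the extremity.* This adds the protocol's trigger and the assessment, and it keeps both the infiltration trigger and the general catch-all. Leave the hemodynamic part of the line and the Patient safety section as they are.

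The cost is one line on the form and possibly a few more incomplete infusions. The sheet already has fields for pause and restart times and asks: "Was the whole infusion given? If not or if paused, please explain why below". Those patients stay in the intention-to-treat analysis.

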Subject exposures: Sequential subject study ID numbers will be randomized in 1:1 ratio to one of two experimental groups. Study drugs will be prepared daily by the research pharmacy and labeled only with the subject ID # and “study drug”. The patient, anesthesiologist, obstetricians, and research staff will remain blinded to assignment. All study subjects will receive standard care with prophylactic oxytocin bolus and infusion, as well as second-line uterotronics on an as-needed basis per institutional protocol. (**Appendix 2**)

- Calcium: 1 gram CaCl₂ in total volume 60mL delivered over 10 minutes beginning 2 minutes after fetal delivery.
- Placebo: 60mL sterile saline delivered over 10 minutes beginning 2 minutes after fetal delivery

Outcomes and Measurement: The primary outcome will be quantitative blood loss (QBL) in mL, which is calculated by standardized methodology including volumetric (suction cannister contents after subtracting amniotic fluid volume) and gravimetric (weighing soiled surgical sponges, drapes, and pads) assessment. Secondary outcomes will include the following: uterine tone assessments by the obstetric attending on a validated 10-point numerical rating scale¹⁴ (NRS_{UT}) at study drug initiation 2 minutes after fetal delivery and reassessed every 5 minutes thereafter until fascial closure. Additionally, total oxytocin bolus and infusion doses, second line uterotronics, change in hematocrit from preoperative to postoperative day one values, total intravenous fluids, and a composite outcome indicating hemorrhage morbidity including transfusion during the hospital stay, hysterectomy, uterine artery embolization, intensive care admission, and death will be recorded.

Please see Appendix 3 for forms to be filled out by research staff.

Data Analysis: Analyses will be conducted using R and supervised by a biostatistical consultant from the Stanford Quantitative Sciences unit. Continuous data will be represented using mean (\pm SD) or median (interquartile range) for variables not normally distributed and compared using parametric or non-parametric t-tests as appropriate. Categorical data will be presented using proportions and compared using a chi-square (or Fishers Exact) test. Two-sided p-values less than 0.05 will be considered statistically significant.

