Venous blood samples for pharmacokinetic analysis: 0.5 mL venous blood will be collected at up to 6 timepoints for willing study participants at each of the following time intervals relative to study drug infusion: baseline (prior to fetal delivery), 0-5 minutes, 5-10 minutes, 10-30 minutes, 30-60 minutes, and 60-240 minutes. Ionized calcium level and pH of blood specimens will immediately be analyzed using an iSTAT machine with a EG7+ cartridge (Abbott Core Laboratory Systems, Lake Forest, IL) in an adjacent operating room by research staff or obstetric anesthesia fellows uninvolved in patient care or data analysis. Venous blood pH and ionized calcium values will be recorded directly into the secure research database but not entered into the patient's medical record as this would compromise blinding. Blood specimens will not be stored.

As a second peripheral IV is frequently placed in the opposite arm from the primary peripheral IV for patients undergoing intrapartum cesarean delivery as part of standard care in case of hemorrhage, this IV will be used for blood collection whenever possible. If not possible to draw blood or this IV is not placed, the patient will be asked for permission to obtain blood specimens using a 22g winged blood collection needle. If possible, these specimens will be collected from the lower extremity (saphenous vein or foot), as these veins are dilated and insensate in patients undergoing cesarean delivery under neuraxial anesthesia. Sterile technique will be utilized for all blood collections.

Pharmacokinetic and pharmacodynamic analysis: We will assess the data with graphical validation to assure data validity. General analyses will be conducted with R statistical programming language (R Foundation for Statistical Computing, Vienna, Austria). PK and PD models will be characterized using nonlinear mixed effects modeling with the program NONMEM 7.4¹⁶.

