We anticipate a two-compartment mammillary model with an effect site. Calcium is administered into the central compartment, also the site of drug sampling. Calcium is also eliminated from the plasma compartment. Calcium may distribute from the plasma compartment to one or more compartments. Drug effect is mediated by the concentration in a hypothetical "effect site", in this case the uterus¹⁷. The effect site permits modeling of hysteresis between the time course of plasma calcium concentration increase and increase in uterine tone measured in Aim 1. PK modeling will be done in the volume and clearance domain and include the influence (if any) of age, weight, gestational age, pH, starting hematocrit, and blood loss.

Equation 1 is an equation for the sigmoidal PD model. Because the measure of drug effect is the NRS_{UT} is an ordinal measure, it will be dichotomized into 4 categories, 0-3, 4-10, 7-10, and 9-10, and modeled as the probability of being in each category as shown in **Figure 2**. PD models will be estimate p_0 , p_{MAX} , C_{e50} , and γ (the baseline probability of uterine tone X, the maximum probability of uterine tone X, the concentration associated with 50% of the change in probability, and the steepness of the concentration versus probability relationship). The effect of pH and uterotonics including oxytocin, methylergonovine, and carboprost on the PD parameters will be explored.

$$p(NRS_{UT} \leq X) = p_0 + (p_{MAX} - p_0) \frac{Ce^{\lambda}}{Ce^{\gamma} + Ce^{\lambda}}$$

Figure 2. PD models will be estimate p_0 , p_{MAX} , C_{e50} , and γ (the baseline probability of uterine tone X, the maximum probability of uterine tone X, the concentration associated with 50% of the change in probability, and the steepness of the concentration versus probability relationship). The effect of pH and uterotonics including oxytocin, methylergonovine, and carboprost on the PD parameters will be explored.

Equation 1: Pharmacodynamic model for the probability of uterine NRS and calcium concentration

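### PK samples can come from different veins, but draw site is neither on the sample form nor in the PK model, so a transit-lag difference between sites would bias V_1 upward and Cl_1 (and Q) downward

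*Combined protocol and SAP*

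**What the plan says.** Specific Aim 2, on venous blood samples, notes that a second peripheral IV in the arm opposite the primary one is often placed "as part of standard care in case of hemorrhage", and that "this IV will be used for blood collection whenever possible". If that IV is absent or will not draw, the patient is asked to allow a winged needle: "If possible, these specimens will be collected from the lower extremity (saphenous vein or foot"). The plan names no site for patients in whom the lower limb is not possible.

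The Patient safety section has the study drug "infused slowly through an intravenous (IV) line in the sensate upper extremity". Subject exposures has it "delivered over 10 minutes beginning 2 minutes after fetal delivery". The post-baseline sampling windows, counted from the start of infusion, are "0-5 minutes, 5-10 minutes, 10-30 minutes, 30-60 minutes, and 60-240 minutes".

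The blood-sample page of Appendix 3 tells staff: "Carefully document the time that the blood was drawn using" the hospital clock. Each sample line then has blanks for time, pH and iCa, and none for limb or vein.

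The PK analysis section anticipates a two-compartment model, takes the sampled blood to be the central compartment, and lists as covariates "age, weight, gestational age, pH, starting hematocrit, and blood loss". A further list, given as examples, does not name draw site either. No lag term appears.

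**The concern.** Calcium enters through an arm vein and rises throughout the infusion. Blood from a vein it reaches later looks like blood drawn earlier. The sample reads low while the infusion runs and slightly high afterwards. The windows 0-5 and 5-10 minutes both lie inside the infusion, where a given time shift changes the reading most.

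If sites with different lags are pooled in a model that assumes none, the fit reconciles the low early values by enlarging the volume and lowering clearance. In a two-compartment model it also lowers the inter-compartmental clearance Q. The plan relies on V_1 to predict the dose needed for a target concentration, and it judges the PK sample size by the precision of V_1. A larger sample narrows the interval but leaves this bias in place.

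**Working it through.** **Inputs from the documents.** Table 2 gives Cl_1 0.93 and V_1 75.6, from a one-compartment pilot model. At N=60, V_1 runs from 62.9 to 84.0 with correction 1.39. The infusion lasts 10 minutes and there are five post-start windows. Table 2 states no units; minutes are assumed for time.

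**Inputs assumed.** The lag is the difference between foot and opposite-arm samples: 0.5, 1 or 2 minutes. The foot share is 30% or 50%. The two-compartment values are V1 25, Q 2 and V1 + V2 = 75.6, so V2 = 50.6.

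**Step 1: the plan's own precision.** (84.0 − 62.9)/75.6 = 27.9%. The correction (n−1)/χ²(0.05, n−1) at n = 60 is 1.39. The product is 38.9%, against 39% in Table 2. Half of that is about ±20%.

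**Step 2: effect on single readings, one-compartment.** During infusion the rise above baseline is proportional to 1 − exp(−kt), with k = 0.93/75.6 = 0.0123 per minute. With lag L the ratio of lagged to true rise is [1 − exp(−k(t−L))]/[1 − exp(−kt)]. At t = 5 and L = 1 this is 0.0480/0.0597 = 0.805, a fall of 19.5%. After the infusion the ratio is exp(kL).

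| Time (min) | Lag 1 min | Lag 2 min |
|---|---|---|
| 2.5 | −39.6% | −79.8% |
| 5 | −19.5% | −39.3% |
| 7.5 | −12.8% | −25.8% |
| 10 | −9.5% | −19.0% |
| 20 | +1.2% | +2.5% |

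**Step 3: effect on the fitted parameters.** Draw times were spread evenly over each of the five windows. Concentrations were generated with the lag at the foot share, then fitted by least squares without it. V_1 bias:

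| Foot share | Lag (min) | One-compartment | Two-compartment |
|---|---|---|---|
| 30% | 0.5 | +1% | +4% |
| 30% | 1 | +2% | +9% |
| 30% | 2 | +5% | +18% |
| 50% | 0.5 | +2% | +7% |
| 50% | 1 | +4% | +14% |
| 50% | 2 | +8% | +29% |

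Repeating this with random draw times and residual noise of 5% of the peak rise gives the same values within about one point. Over these scenarios Cl_1 falls 1% to 8% (one-compartment). In the two-compartment model clearance falls 1% to 5% and Q falls 5% to 30%.

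**Step 4: with site known.** When site is recorded and a site-specific lag is estimated, V_1 bias is within about 1% in every scenario and the lag is recovered (0.98 to 1.01 for a true 1 minute).

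**Step 5: without the early samples.** Fitting only samples after 10 minutes leaves one-compartment V_1 bias under 1%. Two-compartment V_1 bias is within about 2.5%, but Q still falls by 2% to 15%.

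**Step 6: blood loss as a covariate.** A regression of log V on QBL at the 0.05 level assumed 40% foot draws, a QBL SD of 200 mL and an SD of log V of 0.3. With no QBL difference by site, false positives stay near 5%. With 30 calcium patients, an assumed 200 mL difference gives 6% at a log V shift of 0.08, and 14% to 24% at shifts of 0.25 to 0.40.

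**The case against.** The strongest reply is that the size is unproven. No passage gives a lag, a foot share or two-compartment parameters, and the opposite-arm vein has its own transit time, so only the difference between sites counts. In the one-compartment model every scenario in Step 3 is well inside ±20%. Of the twelve entries only one, two-compartment with half the samples from the foot and a 2-minute lag, exceeds it. All of this stands. It limits the size of the point; the gap in the form and model remains.

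Four stronger readings are tempting, and the documents do not support them.

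- A reader might set the 40% or 80% falls in Step 2 against the ±20% for V_1. Those are changes in single readings; the bias in V_1 is much smaller.
- A reader might infer that blood loss will be selected as a covariate because it tracks draw site. That needs an association between site and blood loss. The second IV is described as frequent and as standard care, not as placed by individual risk. The 200 mL difference assumed in Step 6 equals the trial's whole target effect. Without an association the error rate stays near 5%.
- A reader might conclude that site can never be recovered. The paper form lacks the field, but the fields of the research database are not shown.
- A reader might suppose that sampling from the infusion arm is expected. Nothing forbids it, but both stated preferences lead away from it.

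**Conclusion.** The point holds for Aim 2. As written, the plan pools samples from different veins, gives staff no field on the form to tell them apart, and analyses them as one site. Any lag difference between sites biases V_1 upward and Cl_1 downward, with Q also downward in the two-compartment model that the plan anticipates.

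The size is a range that rests on the assumed lag, foot share and minutes as the time unit: about +1% to +8% for V_1 in the one-compartment model, and about +4% to +29% in the two-compartment model with V1 25 and Q 2. The ±20% comparison is indicative for the two-compartment case, because Table 2's V_1 comes from a one-compartment fit. A spurious blood-loss effect is possible only if site is associated with blood loss, which the documents do not show. QBL, tone scores and safety comparisons are untouched. The change is worth making because it is nearly free and because, without a site record, the trial could not show that the bias is negligible.

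**What to change.** 1. Add a draw-site and limb tick box to each sample line in Appendix 3, and a matching database field: opposite-arm IV, foot or saphenous, other vein, infusion arm.
2. Prespecify a test of site in the PK model, as a site-specific lag or as a separate residual error for samples up to 10 minutes, before any other PK covariate is tested.
3. Report a sensitivity fit restricted to opposite-arm samples or to samples after 10 minutes. The opposite-arm fit is the cleaner check on Q (Step 5).
4. Exclude from the PK fit any sample drawn from the infusion arm during the infusion, and report how many there were.

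The cost is one tick box per sample and one extra model term, with no added blood draw or procedure.
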